#### ***7.2 Severity of Adverse Events:***

All AEs will be assessed for their severity and will adhere to the UM IRBMED's standard AE adjudication table. AE severity will be classified as follows:

- Minor: An AE of either no consequence requiring no therapy, or of no consequence requiring only nominal therapy (e.g. overnight hospital admission for observation).
- Major: An AE requiring therapy and a non-complicated hospital stay (<48 hours); requiring major therapy or prolonged hospitalization (>48 hours); causing permanent adverse sequelae; causing death.

#### ***7.3 Reporting Adverse Events:***

If an AE event occurs, it will be documented by a trained member of the study team. The study PI will determine AE severity and relatedness to study. Any AEs related to the study will be reported according to the UM IRBMED's standard AE/ORIO reporting timetable.

### ***8. Statistical Design***

## **A Phase II Randomized Controlled Double-Blind Clinical Trial of Sphenopalatine Ganglion Block for Headache after Concussion**

For the primary outcome, an analysis of covariance (ANCOVA) model will be used to determine treatment effect. The post-treatment headache severity score will be the dependent variable, and the pre-treatment headache severity score and treatment type (lidocaine or placebo) will be independent variables in the model. An ANCOVA model will be used to evaluate for treatment effect in post- vs pre-treatment mean headache severity scores in the 48 hours following the SPG block compared to the 48 hours before the SPG block.

Similar ANCOVA models also will be used to evaluate for between-group treatment effect for the following secondary and exploratory outcomes:

- mean number of days with headache in the one week post-SPG block compared to one week pre-SPG block.
- mean number of headache occurrences within both 48 hours pre- and post-SPG block and one week pre- and post-SPG block
- mean number of headache hours per day within both 48 hours pre- and post-SPG block and one week pre- and post-SPG block
- mean number of as-needed headache treatment uses per day within both 48 hours pre- and post-SPG block and one week pre- and post-SPG block
- mean symptom severity scores in all 22 symptoms on the SCAT5 symptom checklist in both the 48 hours and one week pre-SPG block compared to 48 hours and one week post-SPG block
- mean orthostatic heart rate on standing, and mean orthostatic heart rate change from supine to standing, post-SPG block compared to pre-SPG block
- root mean square of successive differences (RMSSD) post-SPG block compared to pre-SPG block

For the following secondary outcomes, a mixed design analysis of variance (ANOVA) will be used, with a within-subjects factor of time (e.g. pre- vs post-SPG block) and a between-subjects factor of treatment (SPG block with lidocaine vs SPG block with saline):

- mean headache severity score within 15 minutes, 2 hours, 24 hours, and one week post-SPG block compared to immediately prior to procedure, 24 hours, and one week pre-SPG block.
- values on the PGIC rating scale at 2 hours and 24 hours post-procedure in those who received an SPG block with lidocaine compared to a placebo SPG block

For post-hoc analyses, an independent samples t-test (for normal distributions) or Wilcoxon rank-sum test (for non-normal distributions) will be used to compare mean differences, and chi-square tests (for normal distributions) or McNemar's tests (for non-normal distributions) will be used to compare proportional differences.

Participant characteristics will be reported by treatment group, and these will be evaluated for any differences between groups in any characteristic variables, including age, sex, baseline history of migraine, baseline history of depression or anxiety, baseline history of ADHD, previous history of concussions, and referral for cervical and/or vestibular physical therapy. If any differences in these

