## **2. Objective**

The objective of this study is to determine if a SPG block performed after concussion is associated with improvements in post-traumatic headache. The primary outcome will be measured by a reduction in headache severity score of 50% or more in the 48 hours following the procedure compared to the 48 hours prior to the procedure. Secondary objectives will be measured by a reduction in Patient Global Impression of Change rating, number of headache occurrences, days with headache, hours per day with headache, and as-needed headache medication uses. Exploratory objectives are to evaluate if a SPG block improves other non-headache concussion symptoms, as measured by Sport Concussion Assessment Tool version 5 (SCAT5) symptom numbers and severity scores at baseline prior to the procedure and following the procedure; and to evaluate if a SPG block results in improvement in physiologic changes related to potential autonomic nervous system dysfunction due to concussion, as measured by comparisons in orthostatic heart rates and resting heart rate variability recorded prior to and after the procedure.

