## **A Phase II Randomized Controlled Double-Blind Clinical Trial of Sphenopalatine Ganglion Block for Headache after Concussion**

Specific Aim #2: To evaluate the effects of a SPG block on headache frequency and duration after concussion. We hypothesize that patients who receive a SPG block with lidocaine will report less headache days, less headache episodes, and a lower mean number of hours with headache per day than the patients who receive a placebo SPG block in the one week after the SPG block compared to the one week before the SPG block.

Specific Aim #3: To evaluate the effects of a SPG block on as-needed headache treatments after concussion. We hypothesize that patients who receive a SPG block with lidocaine will report a lower mean number of doses of as-needed headache treatments per day than the patients who receive a placebo SPG block in the 48 hours and one week after the SPG block compared to the 48 hours and one week before the SPG block.

Exploratory Aim #1: To evaluate the effects of a SPG block on non-headache concussion symptoms. We hypothesize that patients who receive a SPG block with lidocaine will report lower symptom scores for nausea or vomiting, dizziness, blurred vision, sensitivity to light, and sensitivity to noise than those who receive a placebo SPG block in the 24 hours, 48 hours and one week after the SPG block compared to the 24 hours, 48 hours, and one week before the SPG block.

Exploratory Aim #2: To explore the potential effects of a SPG block on heart rate measurements. We hypothesize those receiving a SPG block with lidocaine will have lower rates of abnormal orthostatic heart rate elevations on standing and higher RMSSD (root-mean square differences of successive R-R intervals) than those who receive a placebo SPG block at 15 minutes following the SPG block compared to before the SPG block.

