## A Phase II Randomized Controlled Double-Blind Clinical Trial of Sphenopalatine Ganglion Block for Headache after Concussion

SPG visit (15 min post- procedure)	x	x	x					x
2h post- procedure	x						x	x
24h post- procedure	x			x	x	x	x	x
Every 24 hours, before the SPG block	x			x	x	x		x

- SCAT5: Sport Concussion Assessment Tool version 5, 22-item symptom checklist, including headache; each symptom rated between 0 and 6.
- oHR: Orthostatic heart rates (HR); HR measured while laying supine at rest, immediately after standing, and after standing for two minutes.
- HRV: R-R interval measured while laying supine at rest
- HA episodes: The number of discrete headache episodes of any duration that occurred during the 24 hour period.
- HA hours: The number of cumulative hours with headache during the 24 hour period.
- # PRN doses: The number of doses of as-needed headache treatments (e.g. acetaminophen, ibuprofen) used during a 24 hour period.
- PGIC: Patient Global Impression of Change, 7-item rating scale ("1" = very much improved, "7" = very much worse)
- AEs: Adverse events

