## **A Phase II Randomized Controlled Double-Blind Clinical Trial of Sphenopalatine Ganglion Block for Headache after Concussion**

characteristics exist between-groups, they will be adjusted for in the analysis as independent variables in the ANCOVA model.

To control for multiple comparisons, a false discovery rate (FDR) will be used. In the event of missing data due to participant withdrawal from study or failure to complete all online survey data, we will use multiple imputation to estimate the missing values. All statistical analyses will be performed using SPSS (IBM, Armonk, NY).

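### Section 8 does not match the exploratory symptom objective: symptom number and the 24-hour window have no analysis, headache is included, and the five named symptoms have no priority

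*Combined protocol and SAP*

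**What the plan says.** Three places describe the same exploratory objective.

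- Section 2 (Objective) sets out to "evaluate if a SPG block improves other non-headache concussion symptoms". Its wording for how this will be judged, before and after the block, is "as measured by Sport Concussion Assessment Tool version 5 (SCAT5) symptom numbers and severity scores".
- Section 3, Exploratory Aim 1, hypothesises "lower symptom scores for nausea or vomiting, dizziness, blurred vision, sensitivity to light, and sensitivity to noise" in the lidocaine arm, "in the 24 hours, 48 hours and one week after the SPG block", each against the matching period before it.
- Section 8 (Statistical Design) lists, for ANCOVA, "mean symptom severity scores in all 22 symptoms on the SCAT5 symptom checklist in both the 48 hours and one week pre-SPG block", compared with the same two periods afterwards.

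The key to the schedule in Section 6.10 describes the SCAT5 instrument as a "22-item symptom checklist, including headache". On multiplicity, Section 8 says: "To control for multiple comparisons, a false discovery rate (FDR) will be used". It gives no level, procedure or family.

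**The concern.** Section 8 as written would not deliver what Sections 2 and 3 promise. One of the two measures in Section 2 and one of the three windows in Aim 1 have no analysis. The item set includes headache although the objective excludes it. The five symptoms in the hypothesis are treated like the other 17.

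The bullet can also be read in two ways: one ANCOVA per item, or one ANCOVA of a mean over 22 items. On the first reading the named symptoms may share a multiplicity adjustment with items outside the hypothesis. On the second they are not tested separately, and a headache effect counts towards a non-headache claim. With 24 participants, leaving this open allows the choice to be made after the data are seen.

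**Working it through.** The plan gives no power or error-rate figure for this analysis. Its sample size (24, 12 per group, 80% power, alpha 0.05) comes without an effect size or SD, so there is no figure to reproduce.

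**1. The sections side by side**

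| | Section 2 | Aim 1 | Section 8 |
|---|---|---|---|
| Measures | symptom number; severity | symptom scores | severity only |
| Symptoms | non-headache (22 − 1 = 21) | five named | all 22, with headache |
| Windows | before and after | 24 h, 48 h, one week | 48 h, one week |

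Section 8 does have a 24-hour analysis of headache severity, but none of the other SCAT5 symptoms.

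**2. Counts on the item-by-item reading**

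- Planned tests: 22 × 2 = 44.
- Tests of named symptoms: 5 × 2 = 10, or 10/44 = 23%.
- Contrasts in Aim 1: 5 × 3 = 15. Section 8 covers 10; the 5 at 24 hours are missing.
- Tests of symptom number: 0.

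**3. Effect of the family size**

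Benjamini-Hochberg at level q rejects the k smallest p-values when the k-th is at most kq/m, for m tests. A lone finding must therefore reach q/m. With q = 0.05 (assumed):

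- m = 44: 0.05/44 = 0.00114
- m = 15: 0.05/15 = 0.0033
- m = 10: 0.05/10 = 0.0050

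**4. Chance of flagging at least one named symptom**

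This is by simulation. Only the 12 per arm comes from the protocol. Assumed: ANCOVA on normal scores, pre/post correlation 0.5, inter-item correlation 0.2 to 0.4, one window, Benjamini-Hochberg at 5%, and an equal effect on all five named symptoms and none elsewhere. The 21 items are the non-headache ones. Ranges cover both inter-item correlations and repeated runs.

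| Improvement in each named symptom | Family of 21 items | Family of the five |
|---|---|---|
| 0.5 SD | about 15–17% | about 34–38% |
| 0.8 SD | about 45–53% | about 71–79% |

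**5. A second check on different assumptions**

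With two windows, simple t-tests and an effect of 1.20 SD (the size that gives 80% power unadjusted at 12 per arm), power per named-symptom test is about 75% in a family of 10 and 47% in a family of 44 if all five respond. If only one responds, it is about 53% and 30%.

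**6. The one-mean reading**

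There are then two tests, one per window, and no dilution by number of tests. Headache enters directly: each point of headache change moves the 22-item mean by 1/22 = 0.045. That is small per point, but it is the symptom the block is meant to relieve.

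**The case against.** The strongest reply is that the outcome is labelled exploratory, that looking across all items is reasonable in a phase II trial, and that multiplicity control is planned. Much of that stands, and it rules out several stronger readings.

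- A reader might infer that Section 8 analyses none of the stated measures. It does analyse severity, and item by item it tests the five named symptoms at two of their three windows.
- A reader might infer that the named symptoms are certain to be swamped. That needs item-by-item testing and a pooled family. The text fixes neither, and a family of the five alone is equally compatible with it. On the one-mean reading there is no such dilution.
- A reader might compare item testing with a single test of a five-symptom sum (46–59% at 0.5 SD, 83–93% at 0.8 SD). That sets an adjusted family against one unadjusted test. With Benjamini-Hochberg over three tests the sum falls to about 28–43% and 68–85%. Equal effects on all five symptoms also favour a sum, and no section defines one.
- A reader might infer a threat to the primary result. There is none unless all outcomes share one false discovery rate family.

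The reply does not supply an analysis of symptom number, a 24-hour contrast, a reason to keep headache, or a choice between the two readings of the bullet.

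**Conclusion.** The mismatch is real and follows from the text alone: symptom number and the five 24-hour contrasts have no planned analysis, headache sits inside a non-headache objective, and the five hypothesised symptoms have no priority among 22.

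The loss of power is conditional. If items are tested one by one in a pooled family, confining the family to the five named symptoms roughly doubles the chance of flagging any of them at 0.5 SD, and raises it by about half at 0.8 SD. Those figures rest on the assumed correlations, FDR level and equal effects, and on a single window; a family spanning two or three windows has a stricter entry threshold. The point is worth correcting before analysis, but it concerns an exploratory outcome.

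**What to change.** Replace the SCAT5 bullet in Section 8 with ANCOVAs of:

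- (a) each of the five symptoms named in Exploratory Aim 1, as their own false discovery rate family with the procedure and level stated, at the windows of the aim. Either add 24 hours to Section 8 or remove it from the aim;
- (b) the number of non-headache symptoms present, range 0–21, stating what rating counts as present;
- (c) the non-headache severity total, range 0 to 21 × 6 = 126.

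Leave headache out of all three. Report the other 21 − 5 = 16 items descriptively with confidence intervals. State the windows for (b) and (c), and state that this family is separate from the primary and secondary outcomes. A five-symptom sum is optional.

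If (b) and (c) use the same windows as (a), this makes 7 × 3 = 21 tests with 24 hours kept, or 7 × 2 = 14 without it, in place of 44.

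The cost is wording only, since the checklist is already completed every 24 hours before and after the procedure. The downside is that effects on the other 16 single items are described, not tested.

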## **3. Specific Aims/Hypothesis:**

Specific Aim #1: To evaluate the effects of a SPG block on headache severity after concussion. We hypothesize that a greater reduction in mean headache severity score in patients who receive a SPG block with lidocaine in the 48 hours after the SPG block compared to the 48 hours before the SPG block. We also hypothesize that patients who receive a SPG block with lidocaine will report lower mean Patient Global Impression of Change (PGIC) scores at two hours and 24 hours post-SPG block compared to those who receive placebo.

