### *6.9 Outcome measures*

## **A Phase II Randomized Controlled Double-Blind Clinical Trial of Sphenopalatine Ganglion Block for Headache after Concussion**

-Primary outcome data points:

1. Headache severity scores: the patient will be asked to use an online survey to report their average daily headache severity score every 24 hours, starting one week prior to the SPG block procedure, until one week following the procedure. They will be asked to rate their headache on a scale of 0 to 6, with 0 corresponding to “absent” and 6 corresponding to “severe.” Additionally, at the SPG block research visit, the patient will be asked to report a headache severity score immediately before the procedure, 15 minutes after the procedure, and two hours after the procedure.

-Secondary outcome data points:

1. Patient Global Impression of Change (PGIC): a rating scale of global improvement with treatment on which participants use a seven-point scale (“1” = very much improved, “4” = no change, “7” very much worse). Using the online survey, participants will rate their change at two hours and 24 hours following the SPG block procedure.

2. Headache frequency/duration: at baseline prior to the procedure, using the aforementioned online survey, the patient will be asked to report the number of headache episodes and hours with headache every 24 hours over the one week prior to the SPG block. Every 24 hours after the SPG, for up to one week after the procedure, as part of the online survey the patient will be asked to record the number of headache episodes and hours with headache in identical fashion.

3. As-needed headache treatment usage: at baseline prior to the procedure, using the aforementioned online survey, the patient will be asked to report the number of uses of as-needed headache medications used every 24 hours in the one week prior to the SPG block. Every 24 hours after the SPG, for up to one week after the procedure, as part of the online survey the patient will be asked to record the number of uses of as-needed headache medications.

-Exploratory outcome data points:

1. Sport Concussion Assessment Tool Version 5 (SCAT5) symptom scores: A symptom checklist survey from the SCAT5 will be given to the patient at baseline at the beginning of the study and every 24 hours during the study period, until one week following the SPG block procedure. From this checklist, the patient will be asked to rate all 22 symptoms on the checklist as 0 (absent) to 6 (severe).

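### Headache severity at 15 minutes, 2 hours and 24 hours is the only listed pre/post outcome given a mixed ANOVA instead of baseline-adjusted ANCOVA, and its time coding and treatment test are left open

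*Combined protocol and SAP*

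**What the plan says.** Section 8 (Statistical Design) sets out the primary model as an ANCOVA in which "the pre-treatment headache severity score and treatment type (lidocaine or placebo) will be independent variables in the model". It then states that "Similar ANCOVA models also will be used to evaluate for between-group treatment effect for the following secondary and exploratory outcomes", and lists seven bullets. One of these covers all 22 SCAT5 symptoms over 48 hours and one week. The key to the schedule table in section 6.10 confirms that headache is one of those symptoms.

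Two secondary outcomes are instead given a mixed ANOVA, "with a within-subjects factor of time (e.g. pre- vs post-SPG block" and a between-subjects factor of treatment. One is PGIC, which has no pre-block value. The other is "mean headache severity score within 15 minutes, 2 hours, 24 hours, and one week post-SPG block compared to immediately prior to procedure". Its full list of comparison times is "immediately prior to procedure, 24 hours, and one week pre-SPG block".

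The baselines exist. Under section 6.9, participants "report a headache severity score immediately before the procedure, 15 minutes after the procedure, and two hours after the procedure", and they "report their average daily headache severity score every 24 hours, starting one week prior to the SPG block procedure". Specific Aim #1 in section 3 hypothesises "a greater reduction in mean headache severity score in patients who receive a SPG block with lidocaine", although that sentence refers to the 48-hour comparison.

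**The concern.** Severity at 15 minutes, 2 hours and 24 hours is treated differently from every other listed outcome that has a baseline, and no reason is given. With 12 participants per arm, a baseline that is already collected is an almost free source of precision.

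Two details are also left open. The bullet names seven times, but the time factor is described only by an example. The analysis could therefore be a set of matched pre/post pairs or one seven-level model. The term that tests treatment is not named either. The two outcomes under this sentence need different terms. For PGIC, which has only post-block values, the treatment main effect is the relevant term. For severity, that effect would average in the pre-block scores, so time-by-treatment is needed.

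Finally, one-week severity has two planned models and no stated precedence.

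**Working it through.** **The plan's own figure.** Section 6.13 states 24 participants (12 per group), 80% power and alpha 0.05. It gives no effect size, SD or correlation, so the figure cannot be reproduced. Solving backwards, 12 per arm gives 80% power for a difference of about 1.20 SD (two-sided t-test). The present point does not depend on this.

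**Inputs.** From the documents: 12 per arm and alpha 0.05. Assumed: a two-sided test, unit SD, an effect of 0.8 SD, and pre/post correlation r = 0.3 / 0.5 / 0.7.

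**Matched-pair layout.** The SDs that enter each test are:
- ANCOVA: √(1 − r²), 21 df.
- Time-by-treatment, which equals a t-test on change: √(2(1 − r)), 22 df.
- Treatment main effect: √((1 + r)/2), 22 df, with the effect halved to 0.4.

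The variance ratio of change score to ANCOVA is 2(1 − r)/(1 − r²) = 2/(1 + r).

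Example at r = 0.5, with √(2/12) = 0.408:
- ANCOVA: 0.8/(0.866 × 0.408) = 2.26.
- Change score: 0.8/(1.000 × 0.408) = 1.96.
- Main effect: 0.4/(0.866 × 0.408) = 1.13.

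| | r = 0.3 | r = 0.5 | r = 0.7 |
|---|---|---|---|
| Variance ratio 2/(1+r) | 1.54 | 1.33 | 1.18 |
| Change-score n per arm to match ANCOVA with 12 (12 × ratio) | 18.5 | 16 | 14 |
| ANCOVA power, noncentral t | 50% | 58% | 74% |
| ANCOVA power, simulated | 48% | 56% | 73% |
| Change-score power | 35% | 47% | 68% |
| Treatment main-effect power | 21% | 19% | 17% |

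The simulated ANCOVA figures are slightly lower because they allow for chance baseline imbalance, so they are the ones to use. At r = 0.8 the noncentral t gives 88% against 84%. With a 1.2 SD effect and r = 0.5 it gives 90% for ANCOVA, 80% for the change score and 37% for the main effect.

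**Seven-level layout** (three pre, four post, equal correlations, constant 0.8 SD effect). The omnibus 6-df interaction has power 58 / 76 / 95%, so it is not weak, but it gives no treatment effect per time point. The main effect has 39 / 29 / 24%. For one joint test on the mean of the four post-block scores, the variances are:
- Post mean minus pre mean: (1 − r)(1/3 + 1/4). At r = 0.5 this is 0.292.
- ANCOVA on the mean of three pre-block scores: (1 + 3r)/4 − 3r²/(1 + 2r). At r = 0.5 this is 0.625 − 0.375 = 0.250.
- ANCOVA on the immediate pre-block score alone: (1 + 3r)/4 − r². At r = 0.5 this is 0.625 − 0.250 = 0.375.

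The corresponding powers at r = 0.3 / 0.5 / 0.7 are about 83 / 93 / 99%, 91 / 95 / 99% and 84 / 85 / 93%. The choice of covariate therefore matters: the immediate score alone does worse than the simple contrast at r = 0.5 and 0.7.

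**Effect confined to 15 minutes and 2 hours.** The omnibus interaction has 50 / 67 / 90%, against 38 / 45 / 62% for the pooled ANCOVA.

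The seven-level figures treat the 24-hour and one-week scores as separate ratings, although these overlap.

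**The case against.** The strongest reply is that a mixed ANOVA is a legitimate analysis of a randomized trial, that its interaction is an unbiased test of treatment, and that only a clarifying sentence is needed. The first two parts stand in full. A reader might infer that the planned test is biased or that the primary result is at risk. Neither follows, because the primary outcome has its own baseline-adjusted ANCOVA.

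A reader might also infer that severity lacks ANCOVA at every time through one week. The SCAT5 bullet rules this out for one week. Nor does the plan leave the times unnamed: all seven are listed, and only their mapping to pairs or levels is missing.

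The low power of the treatment main effect is tempting to present as the plan's expected loss. The documents do not support that. The comparison with pre-block times and the hypothesised greater reduction both point to time-by-treatment. It is the cost of a misreading that the text permits.

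Section 8 also provides post-hoc t-tests or rank-sum tests, which could supply comparisons per time point. They are not tied to this outcome, and no baseline adjustment is described for them.

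The efficiency argument rests on an unknown r. Section 6.4 requires only four or more headaches a week of at least one hour each, so a single rating can fall between headaches and a very high r is unlikely for the 15-minute and 2-hour scores. That is an inference. The daily scores are 24-hour averages, for which r may be higher and the gain smaller.

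**Conclusion.** This is a cheap improvement to a valid secondary analysis, not an error. Severity at 15 minutes, 2 hours and 24 hours is the only listed pre/post outcome without ANCOVA. One-week severity sits under two models, and the time coding and treatment term should be stated.

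In the matched-pair layout, ANCOVA gains about 13, 9 and 5 percentage points of power at r = 0.3, 0.5 and 0.7 (48 − 35, 56 − 47, 73 − 68), and less at higher r. These gains assume 12 per arm, 0.8 SD and two-sided 0.05. The variance ratio 2/(1 + r) depends only on r and on equal pre-block and post-block variances. In the seven-level layout the advantage of a joint ANCOVA holds only if the pre-block mean is the covariate, and it reverses against the omnibus interaction if the effect is confined to the first 2 hours.

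**What to change.** In section 8, state that headache severity at 15 minutes, 2 hours and 24 hours will each be analysed by ANCOVA with treatment and the matching pre-block score. That is the immediate pre-block score for 15 minutes and 2 hours, and the pre-block 24-hour score for 24 hours. Report one-week severity once, from the ANCOVA already planned for the SCAT5 headache item.

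If one joint test is preferred, fit a repeated-measures model to the post-block scores with treatment, time, treatment-by-time and the mean of the available pre-block scores as covariate. Name the treatment effect averaged over time as the test, and report a contrast at each time. Do not use the immediate score alone as covariate. Say whether the one-week score enters, so that it is not tested twice.

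If the mixed ANOVA is kept, state its time levels and name the time-by-treatment contrast as the test for severity.

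The cost is wording only, with no new data or visits. The statistical cost is multiplicity, because separate tests enter the planned false discovery rate control. With Benjamini-Hochberg over four such tests and a constant 0.8 SD effect, per-time power falls from about 48 / 56 / 73% to about 37 / 46 / 67%. Three tests would cost somewhat less, and a wider family could cost more. The joint model avoids this for its main test but is weaker than the omnibus interaction for an effect limited to the first 2 hours.

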#### *6.3 Participants:*

Participants in this study will include patients between 18 and 60 years of age who have been diagnosed with a concussion. Participants will be randomized into one of two groups:

1. Treatment: participants in this group will receive a SPG block using an aqueous 1% lidocaine solution.
2. Control: participants in this group will receive an identical placebo SPG block using a normal saline solution.

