### *6.13 Sample size and power calculation:*

## **A Phase II Randomized Controlled Double-Blind Clinical Trial of Sphenopalatine Ganglion Block for Headache after Concussion**

Sample size calculations were based on previous studies on the use of SPG blocks in acute migraine headache[11] and chronic migraine,[5] in addition to considering the expected recruitment potential from the clinic in the one year study grant period. A sample size of 24 participants (12 per group) was calculated to achieve 80% power with an alpha cutoff 0.05.

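### Post-hoc comparisons of means use a t-test or Wilcoxon test with no baseline covariate, which is less precise than a baseline-adjusted contrast wherever a pre-block value exists

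*Combined protocol and SAP*

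**What the plan says.** The trial has two arms: Section 6.3 states that "Participants will be randomized into one of two groups". Section 6.13 gives the size: "A sample size of 24 participants (12 per group) was calculated to achieve 80% power with an alpha cutoff 0.05".

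Section 8 then sets out three layers of analysis.

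- **ANCOVA.** For the primary outcome the dependent variable is the post-treatment headache score, and "the pre-treatment headache severity score and treatment type (lidocaine or placebo) will be independent variables in the model". For most other outcomes, "Similar ANCOVA models also will be used to evaluate for between-group treatment effect for the following secondary and exploratory outcomes".
- **Mixed ANOVA.** This covers headache severity at 15 minutes, 2 hours, 24 hours and one week after the block, set against values just before the procedure and over the preceding 24 hours and week. It also covers PGIC at 2 and 24 hours.
- **Post-hoc tests.** For means, "an independent samples t-test (for normal distributions) or Wilcoxon rank-sum test (for non-normal distributions) will be used to compare mean differences".

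The post-hoc sentence comes after both model lists. It names no outcomes, no covariate and no criterion for normality. It does not define a mean difference, and it does not say how a post-hoc result relates to the model result. Section 8 closes by naming a false discovery rate, without a family or a level.

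**The concern.** With two arms, the treatment term of an ANCOVA is already the lidocaine-versus-saline comparison, so no pairwise follow-up remains to be done. A t-test or rank-sum test on the same outcome asks much the same question with less information.

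For headache severity at single time points after the mixed ANOVA, a post-hoc contrast does have a purpose. But the pre-block score is collected for every participant, and the stated test does not use it as a covariate.

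Precision is at stake, in a trial of 24 people where little can be spared. The two branches also differ in what they test: the rank-sum test does not compare means, although the sentence gives both branches that label.

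**Working it through.** **1. The plan's own figure.** Section 6.13 gives 24 participants for 80% power at alpha 0.05. It gives no effect size, standard deviation, response rate or sidedness, so the figure cannot be reproduced. Solving backwards for a two-sided t-test with 12 per arm and 80% power gives a standardised difference of 1.197 (1.144 by the normal approximation). An effect of about 1.2 is therefore used below as an assumption.

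**2. Inputs.** From the documents: 12 per arm, two arms, alpha 0.05, headache scale 0 to 6. Assumed: two-sided testing, pre/post correlation r from 0.3 to 0.8, the effect, and a Shapiro-Wilk test at 0.05 to choose between t and Wilcoxon.

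**3. Variance relative to ANCOVA (large sample).** With unit variance before and after, ANCOVA has residual variance 1 − r², a post-score test has variance 1, and a change-score test has 2(1 − r). The ratios to ANCOVA are:

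- post score: 1/(1 − r²)
- change score: 2(1 − r)/(1 − r²) = 2/(1 + r)

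| r | post score | change score |
|---|---|---|
| 0.3 | 1.10 | 1.54 |
| 0.5 | 1.33 | 1.33 |
| 0.7 | 1.96 | 1.18 |
| 0.8 | 2.78 | 1.11 |

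Neither reading of a mean difference reaches ANCOVA's precision. The loss is small for post scores at low r and for changes at high r, and large the other way round.

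**4. Power with ANCOVA power held roughly constant.** Take an effect of 1.2·√(1 − r²), which is 1.2 residual standard deviations. The standardised effect is then 1.2·√(1 − r²) for a post-score test and 1.2·√((1 + r)/2) for a change-score test:

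- r = 0.3: post 1.2 × 0.954 = 1.14; change 1.2 × 0.806 = 0.97
- r = 0.5: post 1.2 × 0.866 = 1.04; change 1.2 × 0.866 = 1.04
- r = 0.8: post 1.2 × 0.600 = 0.72; change 1.2 × 0.949 = 1.14

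Simulation at 12 per arm, on normal data and on scores confined to 0-6, gives about 74-79% power for ANCOVA. The t-or-Wilcoxon rule has about 58-75% on changes and 38-77% on post scores. The 0-6 scores lower ANCOVA power as well, so the bottom of one range should not be set against the top of another. The ends move by a point or two with the way the bounded scores are built.

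**5. Power with the effect fixed at 1.2 post-score standard deviations** (normal data, 10,000 runs per setting):

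| r | ANCOVA | post-score rule | change-score rule | disagrees with ANCOVA at 0.05: post / change |
|---|---|---|---|---|
| 0.3 | 82% | 80% | 66% | 7% / 22% |
| 0.5 | 88% | 80% | 81% | 12% / 12% |
| 0.7 | 97% | 81% | 95% | 17% / 3% |
| 0.8 | 99% | 80% | 99% | 20% / 1% |

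On rounded 0-6 scores the disagreement is 8/12/18/20% for post scores and 27/19/8/3% for changes.

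**6. Type I error of the test choice.** With no effect, the t-or-Wilcoxon rule rejected in 4.7-5.4% of trials in every setting. The choice by distribution does not inflate error.

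**The case against.** The best defence is that Section 8 does not say that these tests are run on the ANCOVA outcomes. The sentence follows the mixed ANOVA list, and post-hoc contrasts after a mixed ANOVA are ordinarily between-arm comparisons at single time points, which repeat no ANCOVA term. This stands as a reading. It does not remove the loss of precision, because headache severity at those time points has pre-block values too.

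Second, a change score does use the baseline. This also stands. A reader might infer that the plan discards baseline altogether, but that is true only if the differences are in post scores. A change score fixes the slope at 1 instead of estimating it, and at high correlation it loses little.

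Third, a reader might infer that the rule leaves two rival verdicts on the treatment effect and so raises the error rate. The documents do not support that. Section 8 names ANCOVA as the test of treatment effect for the primary outcome and the listed others, and labels the remaining tests post-hoc. With no effect, counting a positive result on either test would give about 6-9% error before any FDR adjustment, but no passage allows that.

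Fourth, the low post-score power in step 4 partly reflects how the effect was scaled. With the effect fixed, the post-score rule stays at 80-81%. The ratio to ANCOVA is unchanged, however: in that setting ANCOVA rises from 82% to 99% as r increases.

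**Conclusion.** The point holds as a matter of precision in the post-hoc layer. Where a pre-block value exists, the planned test is less precise than a baseline-adjusted contrast on either reading of a mean difference. The variance is 1.10 to 2.78 times as large for post scores and 1.11 to 1.54 times for changes, over assumed correlations of 0.3 to 0.8. On outcomes already under ANCOVA, it would add a weaker repeat of the treatment term.

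The size depends on the correlation, the effect and the normality rule, none of which the documents give. The direction does not change over the range tried, although at the favourable end of each reading the loss is slight.

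The primary analysis is not affected, and no inflation of type I error follows from the choice of t or Wilcoxon. This is a minor improvement that uses data already planned.

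**What to change.** In Section 8, replace the post-hoc rule for means as follows.

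- For outcomes with a pre-block value, a post-hoc between-arm comparison is the baseline-adjusted ANCOVA difference with its 95% CI at the given time point or window. Name the pre-block value that serves as covariate in each case.
- Outcomes already analysed by ANCOVA get no further unadjusted between-arm test.
- The mixed ANOVA stays as the overall test for multi-time-point headache severity and for PGIC.
- Post-hoc PGIC comparisons at 2 and 24 hours, which have no pre-block value, use the Wilcoxon rank-sum test, named in advance and without a normality check.
- Post-hoc results do not replace the model result.

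This takes a few sentences, with no new data, visits or type of model. The downside is that the baseline-adjusted outcomes lose a rank-based fallback if the scores are badly non-normal.
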